7.2.2.7 QT monitoring

[figure not shown]
QT monitoring will occur as follows:

- On the first day of the first administration of LCI699 (day 1), pre-dose baseline ECGs must be done in triplicate. The mean of the QTcF values from these three ECG tracings is used to determine the mean baseline QTcF.
- On day 1, if the safety ECG (1.5 hours post-first dose of LCI) shows a mean increase in QTcF > 30 ms from the mean baseline value, or the mean QTcF is > 480 ms, then the patient must be discontinued from the study drug according to the discontinuation procedure described in Section 7.1.7 and an unscheduled triplicate ECGs collected at approximately 1-2 hours and a PK sample collected. The patient must remain under observation until the QTcF is < 480 msec and serum electrolytes, calcium, and magnesium are measured and the results normal.
- If at any follow up visit, a QTcF > 480 msec is observed or an increase of the QTcF of >60 msec compared to baseline QTcF assessment, then two additional ECGs, each 2-3 minutes apart, need to be taken after the initial ECG. The mean QTcF from the triplicate ECGs will be determined. If the mean QTcF is > 480 msec or the mean QTcF increase is >60 msec compared to baseline, the patient has to interrupt study treatment while an urgent cardiology consultation is obtained to re-evaluate the ECG and perform a clinical consultation. If immediate treatment is required for patient safety, this should be initiated at the study site without delay and without waiting for confirmation by a cardiologist.

Based on the cardiologist consultation, the following should occur:

- If a mean QTcF > 480 msec is NOT confirmed, no further action needs to be taken. If the cardiologist confirms a mean QTcF > 500 msec, the patient has to discontinue according to the discontinuation procedure described in [Section 7.1.7](#) and an unscheduled PK sample collected. The patient must remain under observation until the QTcF is < 480 msec and serum electrolytes, calcium, and magnesium are measured and the results normal. This observation may be done at the site, in an Emergency Room, or a cardiology clinic, as appropriate and depending upon local resources.
 - a. If the cardiologist confirms that QTcF > 480 msec, LCI699 treatment is temporarily interrupted and a thorough evaluation is performed to assess the patient for acute cardiovascular risk, and for possible underlying heart disease that needs additional evaluation and management. In addition, an unscheduled PK sample will be collected.
 - b. If based upon the assessment by the cardiologist, the investigator considers that there is an acute cardiovascular safety risk and that the patient should not continue with study medication, the patient needs to be discontinued immediately (discontinuation criteria described in [Section 7.1.7](#)).
 - c. If based upon the assessment by the cardiologist, the investigator considers that there is not an acute cardiovascular safety risk; the patient can continue to receive study medication.

Figure 7-2 QT Monitoring Flow Chart (except for Day 1)

* Please refer to [Section 7.1.5](#), study treatment must be discontinued under this circumstance.

7.2.3 Pharmacokinetics

Blood samples for LCI699 PK evaluation will be collected from all patients who receive at least one dose of study treatment. Pharmacokinetic (PK) blood sampling will be performed in each study period as indicated in the Visit Evaluation Schedule ([Table 7-1](#) to [Table 7-3](#)).

Time points of blood sample collection for sparse PK and extensive PK analyses are outlined in [Table 7-10](#) and [Table 7-1](#), respectively. The following PK sampling will be performed:

- Sparse PK assessment in all other patients: trough (predose) and peak (1 – 2 h post-dose). ([Table 7-10](#))

- Extensive PK assessment (subset of n~20 patients): trough (predose), 0.25 – 0.75 h, 1 – 2 h, and 3 – 4 h post-dose during dose titration phase; trough (predose) and peak (1 – 2 h post-dose) beyond titration phase. (Table 7-11)
- [(China only):
 - Extensive sampling: trough (predose), 0.5, 1, 1.5, 2, 4, 6, 8 and 12 h post-dose during dose titration phase if there is a dose escalation; (Table 7-12)
 - Sparse sampling: trough (predose) and peak (1.5 h post-dose) if there is no dose escalation. (Table 7-12)

If LCI administration was interrupted prior to a planned visit and no study treatment is administered on the day of the planned visit, blood draw for PK sampling will not be required.

All ECG procedures should be taken prior to and/or 30 minutes after any PK blood draws since sampling for PK impacts ECG measurements.

Complete dosing information, including the date and time of actual blood draw and time of the last study treatment dose prior to the sampling (24-h clock time), should be obtained on all sampling days and recorded on the PK CRF and/or Contract Research Organization (CRO) requisition form(s). Sampling problems will be noted in the relevant field in the CRF.

An additional blood sample (unscheduled) should be collected in the event that a patient experiences an AE which requires premature termination from the study treatment.

Plasma samples remaining after completion of the determination of LCI699 may be used for exploratory analysis to further characterize the PK of LCI699 and its metabolite(s), such as metabolite profiling, and results will be reported separately.

7.2.3.1 Pharmacokinetic blood collection and handling

Complete instructions for sampling processing, handling and shipment will be provided in the [Laboratory Manual].

Blood samples will be taken by either direct venipuncture or an indwelling cannula inserted in a forearm vein. At specified time points described in Table 7-10 or Table 7-11, blood will be collected into tubes containing K2-EDTA and gently inverted several times to thoroughly mix the anticoagulant. Tubes will be centrifuged to separate plasma and plasma will immediately be transferred into labeled screw-cap polypropylene, cryogenic, freezing vials (e.g. Sarstedt, part# 72.693, no skirt). Plasma samples will be placed in a freezer in an upright position until shipment on dry ice to the Novartis assigned laboratory for analysis.

Table 7-10 Pharmacokinetic blood collection for sparse PK assessment

Visit	Week	Day	Scheduled time point ^a	PK collection number for dose after trough sample ^b	PK collection number prior to trough sample ^b	PK Sample No	Sample volume [mL]
3	0	1	Pre-dose/ 0 h	1		50	2.6
3	0	1	Post-dose 1 - 2 h	1		51	2.6
4	2	15	Pre-dose/ 0 h	2	102	52	2.6
4	2	15	Post-dose 1 - 2 h	2		53	2.6
5	4	29	Pre-dose/ 0 h	3	103	54	2.6
5	4	29	Post-dose 1 - 2 h	3		55	2.6
6	6	43	Pre-dose/ 0 h	4	104	56	2.6
6	6	43	Post-dose 1 - 2 h	4		57	2.6
7	8	57	Pre-dose/ 0 h	5	105	58	2.6
7	8	57	Post-dose 1 - 2 h	5		59	2.6
8	10	71	Pre-dose/ 0 h	6	106	60	2.6
8	10	71	Post-dose 1 - 2 h	6		61	2.6
9	12	85	Pre-dose / 0 h	7	107	62	2.6
9	12	85	Post-dose 1 - 2 h	7		63	2.6
10	16	113	Pre-dose / 0 h	8	108	64	2.6
10	16	113	Post-dose 1 - 2 h	8		65	2.6
11	20	141	Pre-dose / 0 h	9	109	66	2.6
11	20	141	Post-dose 1 - 2 h	9		67	2.6
12	24	169	Pre-dose / 0 h	10	110	68	2.6
12	24	169	Post-dose 1 - 2 h	10		69	2.6
13	26	183	Pre-dose / 0 h	11	111	70	2.6
14	28	197	Pre-dose / 0 h	12	112	71	2.6
15	30	211	Pre-dose / 0 h	13	113	72	2.6
16	32	225	Pre-dose / 0 h	14	114	73	2.6
17	34	239	Pre-dose / 0 h	15	115	74	2.6
18	36	253	Pre-dose / 0 h	16	116	75	2.6
19	40	281	Pre-dose / 0 h	17	117	76	2.6
20	44	309	Pre-dose / 0 h	18	118	77	2.6
777	48	337	Pre-dose / 0 h	---	119	78	2.6
Unscheduled Sample			---	---	---	2001+	2.6

^a The following PK assessment windows are acceptable: pre-dose sample within 0.5 h before dose administration

^b For the PK pre-dose (trough) samples, the actual date and time of administration of the previous dose of study medication should also be recorded with appropriate PK collection number as indicated in the above table. The PK collection number series "1, 2, 3..." is for the LCI699 dose administered on study visit day, while PK collection number series "102, 103, 104..." is for last LCI699 dose the patient received prior to the collection of the PK pre-dose (trough) sample

**Table 7-11 Pharmacokinetic blood collection for extensive PK assessment
(subset of approximately 20 patients)**

Visit	Week	Day	Scheduled time point ^a	PK collection number for dose after trough sample ^b	PK collection number prior to trough sample ^b	PK Sample No	Sample volume [mL]
3	0	1	Pre-dose/ 0 h	201		1	2.6
3	0	1	Post-dose 0.25 - 0.75 h	201		2	2.6
3	0	1	Post-dose 1 - 2 h	201		3	2.6
3	0	1	Post-dose 3 - 4 h	201		4	2.6
4	2	15	Pre-dose/ 0 h	202	302	5	2.6
4	2	15	Post-dose 0.25 - 0.75 h	202		6	2.6
4	2	15	Post-dose 1 - 2 h	202		7	2.6
4	2	15	Post-dose 3 - 4 h	202		8	2.6
5	4	29	Pre-dose/ 0 h	203	303	9	2.6
5	4	29	Post-dose 0.25 – 0.75 h ^c	203		10	2.6
5	4	29	Post-dose 1 - 2 h	203		11	2.6
5	4	29	Post-dose 3 - 4 h ^c	203		12	2.6
6	6	43	Pre-dose/ 0 h	204	304	13	2.6
6	6	43	Post-dose 0.25 – 0.75 h ^c	204		14	2.6
6	6	43	Post-dose 1 - 2 h	204		15	2.6
6	6	43	Post-dose 3 - 4 h ^c	204		16	2.6
7	8	57	Pre-dose/ 0 h	205	305	17	2.6
7	8	57	Post-dose 0.25 – 0.75 h ^c	205		18	2.6
7	8	57	Post-dose 1 - 2 h	205		19	2.6
7	8	57	Post-dose 3 - 4 h ^c	205		20	2.6
8	10	71	Pre-dose/ 0 h	206	306	21	2.6
8	10	71	Post-dose 0.25 – 0.75 h ^c	206		22	2.6
8	10	71	Post-dose 1 - 2 h	206		23	2.6
8	10	71	Post-dose 3 - 4 h ^c	206		24	2.6
9	12	85	Pre-dose / 0 h	207	307	25	2.6
9	12	85	Post-dose 0.25 – 0.75 h ^c	207		26	2.6
9	12	85	Post-dose 1 - 2 h	207		27	2.6
9	12	85	Post-dose 3 - 4 h ^c	207		28	2.6
10	16	113	Pre-dose / 0 h	208	308	29	2.6
10	16	113	Post-dose 1 - 2 h	208		30	2.6
11	20	141	Pre-dose / 0 h	209	309	31	2.6
11	20	141	Post-dose 1 - 2 h	209		32	2.6
12	24	169	Pre-dose / 0 h	210	310	33	2.6
12	24	169	Post-dose 1 - 2 h	210		34	2.6
13	26	183	Pre-dose / 0 h	211	311	35	2.6
14	28	197	Pre-dose / 0 h	212	312	36	2.6
15	30	211	Pre-dose / 0 h	213	313	37	2.6
16	32	225	Pre-dose / 0 h	214	314	38	2.6
17	34	239	Pre-dose / 0 h	215	315	39	2.6
18	36	253	Pre-dose / 0 h	216	316	40	2.6
19	40	281	Pre-dose / 0 h	217	317	41	2.6

Visit	Week	Day	Scheduled time point ^a	PK collection number for dose after trough sample ^b	PK collection number prior to trough sample ^b	PK Sample No	Sample volume [mL]
20	44	309	Pre-dose / 0 h	218	318	42	2.6
777	48	337	Pre-dose / 0 h	---	319	43	2.6
Unscheduled Sample			---	---	---	1001+	2.6

^a The following PK assessment windows are acceptable: pre-dose sample within 0.5 h before dose administration.

^b For the PK pre-dose (trough) samples, the actual date and time of administration of the previous dose of study medication should also be recorded with appropriate PK collection number as indicated in the above table. The PK collection number series "201, 202, 203..." is for the LCI699 dose administered on study visit day, while PK collection number series "302, 303, 304..." is for last LCI699 dose the patient received prior to the collection of the PK pre-dose (trough) sample

^c Required if dose is titrated since last visit. If the LCI699 dose was maintained (i.e. no dose titration since last visit), then only pre-dose and 1- 2 h samples are required.

[(**China only**) For profiles with extensive sampling, the pharmacokinetic parameters ([Table 7-12](#)) of LCI699 will be calculated from individual plasma concentration versus time profiles using non-compartmental analysis (Phoenix WinNonlin v. 6.2). PK parameter derivation will be based on actual time points (elapsed time).

If the LCI699 dose is maintained (i.e. no dose titration since last visit), only pre-dose and 1.5 h samples are required from Visit 5 to Visit 9.]

Table 7-12 [(China only) Pharmacokinetic blood collection for Chinese patients]

Visit	Week	Day	Scheduled time point ^a	PK collection number for dose after trough sample ^b	PK collection number prior to trough sample ^b	PK Sample No	Sample volume [mL]
3	0	1	Pre-dose/ 0 h	401		601	2.6
3	0	1	Post-dose 0.5 h	401		602	2.6
3	0	1	Post-dose 1 h	401		603	2.6
3	0	1	Post-dose 1.5 h	401		604	2.6
3	0	1	Post-dose 2 h	401		605	2.6
3	0	1	Post-dose 4 h	401		606	2.6
3	0	1	Post-dose 6 h	401		607	2.6
3	0	1	Post-dose 8 h	401		608	2.6
3	0	1	Post-dose 12 h	401		609	2.6
4	2	15	Pre-dose/ 0 h	402	502	610	2.6
4	2	15	Post-dose 0.5 h	402		611	2.6
4	2	15	Post-dose 1 h	402		612	2.6
4	2	15	Post-dose 1.5 h	402		613	2.6
4	2	15	Post-dose 2 h	402		614	2.6
4	2	15	Post-dose 4 h	402		615	2.6
4	2	15	Post-dose 6 h	402		616	2.6
4	2	15	Post-dose 8 h	402		617	2.6
4	2	15	Post-dose 12 h	402		618	2.6
If dose is maintained (i.e. no change from visit 4), only take pre-dose and 1.5 h samples							
5	4	29	Pre-dose/ 0 h	403	503	619	2.6
5	4	29	Post-dose 0.5 h ^c	403		620	2.6
5	4	29	Post-dose 1 h ^c	403		621	2.6
5	4	29	Post-dose 1.5 h	403		622	2.6
5	4	29	Post-dose 2 h ^c	403		623	2.6
5	4	29	Post-dose 4 h ^c	403		624	2.6
5	4	29	Post-dose 6 h ^c	403		625	2.6
5	4	29	Post-dose 8 h ^c	403		626	2.6
5	4	29	Post-dose 12 h ^c	403		627	2.6
If dose is maintained (i.e. no change from visit 5), only take pre-dose and 1.5 h samples							
6	6	43	Pre-dose/ 0 h	404	504	628	2.6
6	6	43	Post-dose 0.5 h ^c	404		629	2.6
6	6	43	Post-dose 1 h ^c	404		630	2.6
6	6	43	Post-dose 1.5 h	404		631	2.6
6	6	43	Post-dose 2 h ^c	404		632	2.6
6	6	43	Post-dose 4 h ^c	404		633	2.6
6	6	43	Post-dose 6 h ^c	404		634	2.6
6	6	43	Post-dose 8 h ^c	404		635	2.6
6	6	43	Post-dose 12 h ^c	404		636	2.6

Visit	Week	Day	Scheduled time point ^a	PK collection number for dose after trough sample ^b	PK collection number prior to trough sample ^b	PK Sample No	Sample volume [mL]
If dose is maintained (i.e. no change from visit 6), only take pre-dose and 1.5 h samples							
7	8	57	Pre-dose/ 0 h	405	505	637	2.6
7	8	57	Post-dose 0.5 h ^c	405		638	2.6
7	8	57	Post-dose 1 h ^c	405		639	2.6
7	8	57	Post-dose 1.5 h	405		640	2.6
7	8	57	Post-dose 2 h ^c	405		641	2.6
7	8	57	Post-dose 4 h ^c	405		642	2.6
7	8	57	Post-dose 6 h ^c	405		643	2.6
7	8	57	Post-dose 8 h ^c	405		644	2.6
7	8	57	Post-dose 12 h ^c	405		645	2.6
If dose is maintained (i.e. no change from visit 7), only take pre-dose and 1.5 h samples							
8	10	71	Pre-dose/ 0 h	406	506	646	2.6
8	10	71	Post-dose 0.5 h ^c	406		647	2.6
8	10	71	Post-dose 1 h ^c	406		648	2.6
8	10	71	Post-dose 1.5 h	406		649	2.6
8	10	71	Post-dose 2 h ^c	406		650	2.6
8	10	71	Post-dose 4 h ^c	406		651	2.6
8	10	71	Post-dose 6 h ^c	406		652	2.6
8	10	71	Post-dose 8 h ^c	406		653	2.6
8	10	71	Post-dose 12 h ^c	406		654	2.6
If dose is maintained (i.e. no change from visit 8), only take pre-dose and 1.5 h samples							
9	12	85	Pre-dose/ 0 h	407	507	655	2.6
9	12	85	Post-dose 0.5 h ^c	407		656	2.6
9	12	85	Post-dose 1 h ^c	407		657	2.6
9	12	85	Post-dose 1.5 h	407		658	2.6
9	12	85	Post-dose 2 h ^c	407		659	2.6
9	12	85	Post-dose 4 h ^c	407		660	2.6
9	12	85	Post-dose 6 h ^c	407		661	2.6
9	12	85	Post-dose 8 h ^c	407		662	2.6
9	12	85	Post-dose 12 h ^c	407		663	2.6
10	16	113	Pre-dose / 0 h	408	508	664	2.6
10	16	113	Post-dose 1.5 h	408		665	2.6
11	20	141	Pre-dose / 0 h	409	509	666	2.6
11	20	141	Post-dose 1.5 h	409		667	2.6
12	24	169	Pre-dose / 0 h	410	510	668	2.6
12	24	169	Post-dose 1 - 2 h	410		669	2.6
13	26	183	Pre-dose / 0 h	411	511	670	2.6
14	28	197	Pre-dose / 0 h	412	512	671	2.6
15	30	211	Pre-dose / 0 h	413	513	672	2.6
16	32	225	Pre-dose / 0 h	414	514	673	2.6
17	34	239	Pre-dose / 0 h	415	515	674	2.6
18	36	253	Pre-dose / 0 h	416	516	675	2.6
19	40	281	Pre-dose / 0 h	417	517	676	2.6
20	44	309	Pre-dose / 0 h	418	518	677	2.6

Visit	Week	Day	Scheduled time point ^a	PK collection number for dose after trough sample ^b	PK collection number prior to trough sample ^b	PK Sample No	Sample volume [mL]
777	48	337	Pre-dose / 0 h	---	519	678	2.6
Unscheduled Sample			---	---	---	3001+	2.6

^a The following PK assessment windows are acceptable: pre-dose sample within 0.5 h before dose administration, ±10 min for up to the 2 h time points; ± 30 min for time points beyond 2 h.

^b For the PK pre-dose (trough) samples, the actual date and time of administration of the previous dose of study medication should also be recorded with appropriate PK collection number as indicated in the above table. The PK collection number series "401, 402, 403..." is for the LCI699 dose administered on study visit day, while PK collection number series "502, 503, 504..." is for last LCI699 dose the patient received prior to the collection of the PK pre-dose (trough) sample

[figure not shown]
^c Required if dose is titrated since last visit. If the LCI699 dose was maintained (i.e. no dose titration since last visit), **then only pre-dose and 1.5 h samples are required.**

[figure not shown]
Table 7-13 [(China only) Non-compartmental pharmacokinetic parameters]

AUC _{last}	The area under the concentration-time curve from time zero to the last measurable concentration [ng*h/mL]
AUC _{inf}	The area under the plasma concentration-time curve from time zero extrapolated to infinity when feasible [ng*h/mL]
C _{max}	The maximum (peak) plasma concentration after single dose administration [ng/mL]
T _{max}	The time to reach maximum plasma concentration following drug administration [h]
T _{1/2}	The elimination half-life [h]
Cl/F	Apparent systemic clearance of drug from plasma [L/h]
V _z /F	Apparent volume of distribution during terminal phase [L]

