1.2.1.2 Clinical experience

1.2.1.2.1 Summary of clinical pharmacokinetics

The pharmacokinetics of LCI699 has been studied in healthy volunteers, patients with hypertension, and patients with hyperaldosteronism, as well as in an ongoing proof-of-concept study in Cushing's disease patients. For detailed information, please refer to the [Investigator's Brochure].

Following single oral doses of 0.5 mg to 200 mg to healthy volunteers under fasting conditions, LCI699 was rapidly absorbed with a Tmax of approximately 1 hour, consistent at all doses studied. The elimination half-life of LCI699 was 3-5 hours across all doses examined. About 6% of the dose is excreted unchanged in the urine. The pharmacokinetics of LCI699 were over-dose proportional in the dose range of 0.5 to 200 mg (single dose); for a 2-fold increase in dose, the AUC increase would be about 2.4-fold, and Cmax increase would be 2.1-to 2.4-fold [LCI699A2101].

Due to its short elimination half-life, LCI699 does not accumulate in plasma following twice-daily multiple dosing up to 3 mg b.i.d., and there is no change in the kinetics on repeated dosing. Accumulation ratio based on AUC (Day 1 vs. Day 14) is 0.8 - 1.3 in subjects dosed with ≤ 3 mg b.i.d. Typically, the coefficient of variation for plasma LCI699 AUC is in the region of 11 - 40% in healthy subjects after an oral dose [LCI699A2101].

For exploratory assessment of food effect, pharmacokinetics of a single oral dose of 100 mg LCI699 under fasting conditions was compared with that following a high fat meal in the first-in-human study (n=3 - 5). Administration of 100 mg LCI699 with a high fat meal resulted in a reduction in AUC and Cmax by 14% and 25%, respectively, and the median Tmax was delayed from 1 h to 2.5 h after high fat meal. The impact is not considered clinically significant; the delay in Tmax and impact on Cmax is expected as food delays gastric emptying and prolongs intestinal transit time.

Impact of ethnic origin on LCI699 pharmacokinetics was investigated in Caucasian and Japanese healthy male subjects following single and multiple doses of LCI699 (0.25, 0.5, 1, 2 mg). LCI699 exposure (AUC) was 18%, 44%, and 66% higher in Japanese healthy volunteers in comparison to Caucasians after single dose of 0.5 mg, 1 mg and 2 mg LCI699, respectively,

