6.1.1 Dosing regimen

The dosing regimen of LCI699 in the planned pivotal study will be up-titrated according to the following escalation sequence: LCI699 2 mg b.i.d., 5 mg b.i.d., 10 mg b.i.d., 20 mg b.i.d., and 30 mg b.i.d. The up-titration continues till the mUFC \leq ULN. The maximum dose of LCI699 in this study is 30 mg b.i.d.

Study treatment should be taken twice daily (b.i.d.). For example, a patient on the starting dose of 2 mg b.i.d. dose will take two tablets of 1 mg strength in the morning and two tablets of 1 mg strength in the evening, providing a total daily dose of 4 mg. Study drug should be taken at approximately the same time each day, with about 12 hours between each dose administration. LCI699 can be dosed without regard to food. If vomiting occurs during the course of treatment, patients should not take the study drug again before the next scheduled dose. Patients should be instructed not to make up missed doses.

On study visit days, patients should be reminded to not take the study treatment prior to the site visit to ensure compliance with the pre-dose PK sampling procedure. The morning dose on the visit days should be taken at the site after the pre-dose PK sampling.

Triplicate urine samples are collected every two weeks during individual dose titration with the last urine sample preferably collected the day prior to the visit at site.

- The LCI699 dose is increased if the mean of three urine samples (mUFC) is above normal ($>$ ULN).
- The LCI699 dose is maintained if the mUFC value is in the normal range and the patient does not have signs or symptoms of hypocortisolism or adrenal insufficiency.
- The LCI699 dose is reduced if the mUFC value is $<$ LLN or the patient has signs and symptoms of hypocortisolism or adrenal insufficiency and the mUFC value is in the lower part of the normal range.

Hypocortisolism or adrenal insufficiency is suspected on the basis of clinical signs/symptoms, which may include gastrointestinal symptoms (nausea, vomiting), fatigue, weakness, failure to thrive, morning headache, symptoms consistent with hypoglycemia, or dizziness.

Dose reductions and temporary dose interruptions for safety reasons are permitted at any time during the study. For patients that enter the randomized withdrawal period, both the investigator and the patient are blinded to the randomized treatment assignment from the time of randomization until the time of database lock for the core period of the study.

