10.5.4 Pharmacokinetics

The PAS will be used in all pharmacokinetic data analysis and summary statistics.

As sparse pharmacokinetic sampling is performed in this study, traditional non-compartmental analysis will not be performed to calculate pharmacokinetic parameters. Plasma concentration data of LCI699 will be listed by patient, visit, incident dose and nominal sampling times. Descriptive statistics of plasma concentrations will be provided by incident dose, visit and nominal sampling times. Graphical depiction (mean and individual) for LCI699 concentrations and/or profiles (if applicable) during the course of the study will be performed by incident dose and visit. Additional details on PK data analysis will be specified in the SAP.

PK data generated from this study will be used in conjunction with PK data from other clinical studies in population PK assessment. Patient demographics (e.g. age, gender, ethnicity, weight) will be explored as covariates, if appropriate. The broad principles outlined in the FDA “Guidance for Industry: Population Pharmacokinetics” will be followed during the population PK analysis. The results of population PK assessment will be presented in a separate report.

[(China only) Plasma concentration data of LCI699 will be listed by patient, visit, incident dose and nominal sampling times. Descriptive statistics of plasma concentrations will be provided by incident dose, visit and nominal sampling times. For the extensive sampling profiles, graphical depiction (mean and individual) for LCI699 concentrations and/or profiles (if applicable) during the course of the study will be performed by incident dose and visit. Descriptive statistics will be reported for all PK parameters (including AUC_{last}, AUC_{inf}, C_{max}, T_{max}, T_{1/2}, Cl/F, V_z/F) for LCI699 from the extensive sampling profiles. For sparse sampling data, traditional non-compartmental analysis will not be performed. PK data from this study will be used in conjunction with PK data from other clinical studies in population PK assessment.]

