1.1 Protocol amendments

At the time of finalization of this document the original study protocol had undergone five amendments, as summarized below.

Amendment 1, 15-JUL-2014

The purpose of this protocol amendment is to address requests from the Voluntary Harmonization Procedure (VHP) review. Changes made to the protocol during this amendment were summarized below:

- The definition of the optional extension period was revised to specify the length of study treatment.
- The definition of time-to-escape (one of the secondary objectives) was clarified.
- To ensure that pregnancy was identified as an absolute withdrawal criterion, it was moved from the list of general study withdrawal criteria to the list of study specific criteria that require study treatment discontinuation.
- To harmonize with ICH guidelines, treatment discontinuation criteria was revised to include an increase in QTcF > 60 msec from pre-first dose baseline measurement.
- To improve monitoring for potential QT prolongation, 24-hour Holter recordings were added during the extension at Weeks 72 and 96. As a result of this addition, both the Visit Evaluation Schedule and the ECG Collection Table were also revised.

Amendment 2, 11-Mar-2015

The primary reason for this amendment is to add a local, country-specific intensive PK sampling for China in order to investigate potential ethnic differences in LCI699 pharmacokinetics at steady-state and at doses used in the treatment of patients with Cushing's disease.

Additional changes applicable to all countries include:

- Inclusion of recent LCI699 clinical trial results information (longer-term safety and efficacy data (LCI699C2201) and results of the clinical drug-drug interaction study (LCI699C2102)).
- Relaxation of the protocol guidance on narrow therapeutic index/sensitive substrates of CYP1A2, CYP2C19, CYP2D6 and CYP3A4/5 as concomitant medication (based on the results of the clinical drug-drug interaction study (LCI699C2102)).
- Blinding: The pharmacist, the bioanalyst and the pharmacokineticist are also blinded.
- Inclusion criteria:
 - Minimum period since last stereotactic radiosurgery decreased from 3 to 2 years.
 - Rescreening is introduced, some therapies needed washouts are removed and the screening period is extended to accommodate for the need for long washout periods.
- Exclusion criteria:
 - QTcF exclusion limits tightened from >470 ms to >450 ms (males) and >460 ms (females).

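### The China PK plan applies a single-dose parameter list to profiles taken on repeated 12-hourly dosing, so AUCinf after Day 1 overstates per-dose exposure by about 7% to 24%

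*Protocol*

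**What the plan says.** The China sampling was added to "investigate potential ethnic differences in LCI699 pharmacokinetics at steady-state" (SAP 1.1, on Amendment 2).

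Protocol Table 7-12 schedules nine samples from pre-dose to 12 h at Visit 3 (Day 1) and Visit 4 (Day 15). The same full set is taken at Visits 5 to 9 only if the dose was titrated since the last visit. Otherwise those visits have a pre-dose and a 1.5 h sample. From Visit 10 onward sampling is sparse or pre-dose only.

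Table 7-13 lists AUClast, AUCinf, Cmax, Tmax, T1/2, Cl/F and Vz/F. AUCinf is "The area under the plasma concentration-time curve from time zero extrapolated to infinity when feasible [ng*h/mL". Cmax is "The maximum (peak) plasma concentration after single dose administration [ng/mL". The table names no AUC over the dosing interval and no steady-state clearance, and it gives no formula for Cl/F or Vz/F.

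Section 10.5.4 applies the list to all the extensive China profiles: "Descriptive statistics will be reported for all PK parameters". It excludes non-compartmental analysis of sparse data and leaves further PK detail to the SAP. The SAP supplied covers the Final CSR only and plans no PK analysis (SAP 2.9). The core-phase SAP, dated 06-Jul-2018, is not among the documents.

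**The concern.** After a first dose, AUC from zero to infinity measures the exposure from that dose. At steady state under linear kinetics, the same quantity is the AUC over one dosing interval. Extrapolating a steady-state profile to infinity adds a tail that belongs partly to earlier doses, so AUCinf is too large. A clearance or volume computed from it is too small.

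The clearest consequence is in the comparison of Visit 3 with Visit 4. Protocol 4.1.1 does not allow a dose increase at Week 0 or Week 2, so both profiles are normally at the same dose. A patient whose clearance has not changed would show an artificial rise in AUCinf between them.

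Comparing Day 1 with a profile after a dose increase has a related problem. Protocol 1.2.1.2.1 reports that AUC rises about 2.4-fold per doubling of dose, which is 2.4/2 = 1.20, or 20% after dose normalization. The artefact has the same direction and a similar size, so AUCinf alone could not separate the two.

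**Working it through.** The documents give no figure for this bias, so there is none to reproduce.

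**Inputs**
- Half-life: "The elimination half-life of LCI699 was 3-5 hours across all doses examined" (Protocol 1.2.1.2.1).
- Dosing interval of 12 h: "with about 12 hours between each dose administration" (Protocol 6.1.1).
- Absorption: "LCI699 was rapidly absorbed with a Tmax of approximately 1 hour" (Protocol 1.2.1.2.1, fasting).
- Sampling times: 0, 0.5, 1, 1.5, 2, 4, 6, 8 and 12 h (Table 7-12).
- Assumption: linear one-compartment kinetics.

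**Is steady state reached?** Five half-lives are 5 × 3 = 15 h to 5 × 5 = 25 h. A patient on unchanged dosing is well past that by Day 15. So is a patient titrated between visits who has taken the new dose for more than about a day.

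**Instant absorption.** Let λ = ln 2 / half-life and τ = 12 h. At steady state AUC0-12 = Dose/(CL/F), and extrapolation adds C12/λ. Then

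AUCinf / AUC0-12 = 1 / (1 − exp(−λτ)),

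and Dose/AUCinf falls short of CL/F by the fraction exp(−λτ). Vz/F = Dose/(λz × AUCinf) falls short by the same fraction.

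**First-order absorption.** The rate ka is set so that ln(ka/λ)/(ka − λ) = 1 h, which gives 2.68, 3.04 and 3.31 per h for half-lives of 3, 4 and 5 h. The ratio is 1 + C12/(λ × AUC0-12).

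| Half-life | exp(−λ × 12) | AUCinf/AUC0-12, instant | Clearance shortfall | AUCinf/AUC0-12, Tmax 1 h | Clearance shortfall |
|---|---|---|---|---|---|
| 3 h | 0.0625 | 1.067 | 6.25% | 1.073 | 6.8% |
| 4 h | 0.125 | 1.143 | 12.5% | 1.15 | 13.2% |
| 5 h | 0.189 | 1.234 | 18.9% | 1.244 | 19.6% |

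AUCinf is therefore about 7% to 24% too high, and an AUCinf-based clearance about 6% to 20% too low.

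**With the planned samples.** Trapezoidal calculation on the Table 7-12 times (Tmax 1 h, linear and linear-up/log-down rules) gives AUCinf at 1.059 to 1.243 times the true per-dose exposure. AUClast to 12 h gives 0.986 to 1.004 times the true value. On Day 1, AUCinf is 0.986 to 0.990 times the true value (linear-up/log-down rule), so it is sound there.

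**Sensitivity.** With the fed Tmax of 2.5 h from Protocol 1.2.1.2.1, the ranges become 10% to 28% for AUCinf and 9% to 22% for clearance.

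**Consistency check.** The Tmax 1 h model predicts an AUC accumulation ratio of 1.07 to 1.25. The protocol reports: "Accumulation ratio based on AUC (Day 1 vs. Day 14) is 0.8 - 1.3 in subjects dosed with" doses up to 3 mg b.i.d. The model lies inside that range.

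**The case against.** The strongest reply is that the interval AUC is already there under another name. AUClast runs to the last measurable concentration, and the last planned sample is at 12 h. The quantification limit is 0.10 ng/mL, and the lowest trough cited in patients is 0.336 ng/mL, after 2 mg b.i.d. The 12 h value should normally be measurable, so AUClast is in effect AUC0-12. This stands, and it limits the point to AUCinf and whatever is derived from it. It does not remove the point. AUClast ends at the actual sampling time (12 h ± 30 min), is not named as the basis for Cl/F or Vz/F, and does not correct the AUCinf that 10.5.4 also requires.

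Second, no formula for Cl/F or Vz/F is written. The bias in those two is therefore conditional.

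Third, the core-phase SAP may define the parameters by visit. That cannot be checked here.

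A reader might also infer more than the documents support:
- *That every visit after Day 1 is affected.* Full profiles exist only at Visit 4 and, after titration, at Visits 5 to 9. No non-compartmental analysis is done on sparse data.
- *That the bias would pass for an ethnic difference.* Protocol 1.2.1.2.1 cites 18% higher AUC in Japanese than in Caucasian volunteers at 0.5 mg, which is within the size of the bias. The same sentence gives 44% at 1 mg and 66% at 2 mg, and this trial starts at 2 mg b.i.d. The documents plan no comparison of China non-compartmental clearance with another group. Other patients get no such analysis, and ethnicity is to be explored as a covariate in population PK, which uses the PK data themselves.

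**Conclusion.** The point holds in a limited form. Table 7-13 and section 10.5.4 require a first-dose exposure measure for profiles that are essentially at steady state, in a sampling plan meant to study steady state. As written, AUCinf at Visit 4 and at titrated Visits 5 to 9 overstates per-dose exposure by about 7% to 24%. Cl/F and Vz/F would be about 6% to 20% too low if derived from it.

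These sizes rest on linear one-compartment kinetics, a half-life of 3 to 5 h, a 12 h interval and a Tmax near 1 h. The protocol reports over-proportional exposure across doses, so they are approximate.

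The scope is a descriptive PK analysis in one country. No efficacy or safety conclusion, hypothesis test or sample size depends on it.

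**What to change.** In Table 7-13 and the China paragraph of 10.5.4:
- Report AUCinf, and Cl/F and Vz/F based on it, for Visit 3 only, and state the formulas.
- For extensive profiles at Visits 4 to 9, report AUC0-12 (AUCtau), CLss/F = Dose/AUC0-12 and Vz/F = Dose/(λz × AUC0-12).
- Drop the single-dose wording from Cmax at those visits.
- Summarize Day 1 and steady-state parameters separately.
- Correct the cross-reference in 7.2.3.1 that points to Table 7-12 for the parameters; they are in Table 7-13.

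If the core-phase SAP already defines these parameters, align the protocol table and 10.5.4 with it.

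The cost is wording in one table and one paragraph, and a change of parameter settings in the non-compartmental software. The planned 0 to 12 h samples recover AUC0-12 to within about 1.5% under the model above, so no extra samples or patients are needed.
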